#### 10.3. Unanticipated Problems

Any unanticipated problem involving subjects or others will be reported to the IRB, such as protocol violations or deviations as required by the IRB reporting procedures.

### 11. SUPPORTING DOCUMENTATION AND OPERATIONAL CONSIDERATIONS

#### 11.1. Measures Taken to Protect the Rights and Welfare of Subjects

11.1.1. All subjects will be monitored closely throughout the study. There will be an ACLS certified medical doctor present in the study area throughout the study.

11.1.2. The following measures will be taken to ensure the confidentiality of the subjects:

11.1.2.1.A code (identification) number for each subject will be kept on file.

11.1.2.2.Only their corresponding identification number will identify subjects.

11.1.2.3. Access to identifying documents (IC, SSN, photo ID) and data will only be made to the principal investigators in the study and study staff.

11.1.2.4. The confidentiality and retention of these documents will be protected to the extent provided and required by the law.

11.2. Vulnerable Populations

11.2.1. Employees are considered to be a vulnerable population.

Participation is not a condition of employment. There will be no repercussions in the workplace in the case that the employee refuses to participate in the study or withdraws at any point during the study. Neither supervisors nor superiors will be involved in the recruitment of employees for participation in the study.

11.2.2. Economically disadvantaged or unemployed and educationally disadvantaged

Reasonable compensation will be provided for economically disadvantaged subjects to eliminate possibility of undue influence due to financial incentive. Educationally disadvantaged subjects will be provided ample time to ask questions and comprehend information.

11.3 Documents and Database

Documents will be kept a minimum of 5 years after the specific product/tested for is no longer being made. If destroyed, these documents will be shredded and done by a certified company used for destroying medical and clinical data

Documents and information stored electronically will be protected using a multi-faceted procedure including, but not limited to the following steps:

- Two layers of endpoint security and one layer of DLP (Data loss prevention) running on all company machines.
- Premier firewalls/Network monitoring appliances and log collection systems (SIEM) protecting the network.
- 4 layers of email security systems for protecting against phishing attacks.
- Security policies to limit access to specific folders.

12. DEVICE ACCOUNTABILITY

12.1. Receipt of Study Device

Upon receipt of the study device supplies, an inventory must be performed and the device accountability log filled out and signed by the person accepting the shipment. It is important that the designated study staff counts and verifies that the shipment contains all the items noted in the shipment inventory. Any damaged or unusable study devices in a given shipment will be documented in the study files.

12.2. Use of Study Device

Use of devices and sensors will be documented on case report forms for each subject.

12.3. Return or Destruction of Study Device

At the completion of the study, there will be a final reconciliation of study devices and sensors shipped, devices/sensors used, and devices/sensors remaining. This reconciliation will be logged on the device accountability

log. Any discrepancies noted will be investigated, resolved, and documented prior to return or destruction of unused study devices. Devices destroyed on site will only be upon written instruction from the sponsor and will be documented in the study files.

### 13. RISKS AND BENEFITS

- 13.1. Benefits: There would be no other benefit to the subject. Other possible benefits would be to society as a whole. Evaluation of the accuracy of this new device could enable healthcare workers to more appropriately treat potentially life threatening conditions.
- 13.2. Device Risks: The noninvasive devices used in this study are similar in technology and design to some commercially available pulse oximeters and other non-invasive devices and hence have the same risks. Pulse oximeters and other non-invasive devices are commonly used and are considered to be minimal risk. There is an extremely small risk of damage to the subject's fingers, or other locations where sensors are placed, from the device including temporary skin irritation or discomfort associated with exposure to the sensor as well as potential temporary mechanical irritation or discomfort. There is a remote, yet possible, risk of a burn from the sensor. In the case of a sensor burn there is the potential for permanent skin damage (scar/discoloration).
- 13.3. Venous Cannulation Risks: bleeding, swelling, infection, infiltration of fluids/ blood into area surrounding IV, bruising, hematoma, damage to the blood vessel and surrounding nerves or tissue.
- 13.4. Arterial Cannulation risks: bleeding, infection, hematoma, damage to the blood vessel and surrounding nerves, tendons or tissue; loss of feeling in hand and/or arm and even the loss of hand due to rare complications of the study.
- 13.5. Risks Associated with Removal of Blood: Removal of blood is generally considered to be safe in most patients and exceptionally safe in healthy volunteers (i.e. blood donation). The risk of removing blood includes the risks obtaining venous access. Additionally, there is the risk of hypotension, tachycardia, anemia, dizziness and loss of consciousness. All subjects will be maintained in a reclined position throughout the study and a physician will be available to continually monitor the vital signs.
- 13.6. Blood Draw risks: discomfort is generally associated with needle puncture. The most common complications associated with blood draws and capillary sticks are hematomas or bruising. All blood draws will be performed by qualified personnel. An ACLS certified physician will be in attendance throughout the entire procedure, and the study will be completed under their general supervision. Other anticipated adverse events that may occur, include but are not limited to: Vaso vagal (passing out), infiltrated IV, lightheadedness, feeling flush/ warm, feeling nauseated, throwing up, seizures, sudden drop in blood pressure/ sudden increase in blood pressure, sudden drop in heart rate/ sudden increase in heart rate, tingling sensation of face/arms and/or sweating, and mouth dryness. These anticipated adverse events are expected to be temporary.
- 13.7. Risk From Hemodilution: Hemodilution has been used successfully as a technique to reduce perioperative blood loss during surgery. Hemodilution is generally considered to be safe in most patients and exceptionally safe in healthy volunteers. In surgery, the chief benefit of hemodilution is the reduction of blood losses when whole blood is shed perioperatively at lower hematocrit levels after hemodilution is completed. In our controlled clinical lab, withdrawal and blood loss will be limited to samples required for laboratory analysis; hemodilution will be used principally to lower the subject's hematocrit and hemoglobin. The risks of hemodilution include heart failure, respiratory failure, hypertension, edema, infection and electrolyte abnormalities. Isotonic fluids will

be administered. A physician will be immediately available thorough out the procedure and vital signs will be continually monitored.

13.8. Risk from Inflicted Knowledge: The risk of inflicted medical knowledge to volunteers is negligible since we deidentify all associated sample information including those relevant to our clinical and engineering parameter studies. The monitoring and test results are not examined for diagnostic purposes and do not reflect an attempt to ascertain any subject's medical condition. The attending physician's role during this study is to ensure the safety of the subject during the study. Subjects are informed that these are not diagnostic tools, if observations are made using FDA cleared devices we will refer them to their primary care physician.

13.9. Risk From Loss of Confidentiality: Masimo upholds the highest standards to protect hard and electronic data however a complete promise for confidentiality cannot be guaranteed due to unforeseeable events.

13.10. Risk From Additional Testing:

During the conduct of the study, it is possible, but not likely, that someone could become exposed to the sample of blood drawn from the subject through an inadvertent needle stick or by contact with an open cut. In such circumstances, it will be important to the exposed individual to know whether the blood to which he or she was exposed contained Hepatitis B virus (HBV), Human immunodeficiency virus (HIV), or Hepatitis C virus (HCV) and additional testing of the sample will be performed.

Within the consent subjects will agree to permit the company to test the blood sample (or samples) by signing the consent. The test results will be maintained as confidential and will only be used by healthcare professionals for the diagnosis and treatment of the exposed individual as appropriate.

In the case that Masimo needs to contact a subject regarding additional testing they will be contacted by a Masimo employee and medical personnel can be available for further counsel if requested.

The cost for the initial testing and compensation for their time/travel to the testing facility will be the only things paid for by Masimo.

13.11. Lidocaine (injection) Risks: Insertion of the Lidocaine may be discomforting and can feel like a slight pinch along with a warm/burning sensation. Other anticipated adverse events that may occur, include but are not limited to: Flushing or redness of the skin, itching skin, small red or purple spots on the skin, unusually warm skin, bruising, bleeding at the application site, swelling. These adverse events are expected to be temporary.

13.12. Although not common, it is also possible to have an allergic reaction to injectable lidocaine. Subjects should not take part in this study if they are allergic to lidocaine injection or other types of numbing medicine, or if they have a heart rhythm disorder such as Wolff-Parkinson-White Syndrome or Stokes-Adams syndrome. Subjects are instructed to tell the study staff right away if they experience hives; difficulty breathing; swelling of your face, lips, tongue or throat.

13.13. Ethyl Chloride (Lidocaine Spray): Ethyl Chloride is a topical anesthetic which is used to prevent pain by cooling the skin. Although unlikely, the anticipated adverse events that may occur, include but are not limited to: changes in skin color (i.e. Flushing or redness of the skin), delayed wound healing, rash, itching and swelling. These adverse events are expected to be temporary.

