7. PROCEDURE

7.1. SCHEDULE OF ACTIVITIES

Procedures	Phone Pre-Screen	Baseline Visit 1	Procedure Visit 1
Brief Study Procedure Description	X		
Informed consent		X	
Demographics (including skin tone)	X	X	
Medical history (subject-reported)	X	X	
Concomitant medication review	X	X	
Vital Signs (ECG, Blood Pressure Cuff, Pulse Ox)		X	X
Height	X	X	
Weight	X	X	
ASA Status Assessment		X	
Pregnancy test 		X	
Allen’s Test		X	
Venous sample (via needle stick or IV placement)		X	

Procedures	Phone Pre-Screen	Baseline Visit 1	Procedure Visit 1
Local anesthetics (lidocaine, ethyl chloride spray, or pain ease skin refrigerant) as needed 		X	X
Peripheral Venous Line (IV) 		X	X
Intra-arterial catheter (A-line)			X
Placement of test and control sensors			X
Noninvasive data collection			X
Removal of Blood (if necessary)			X
IV Fluid Administration			X
Continuous A-line sampling			X
Line Removal			X
Post Care Instructions Given		X	X
Discharge		X	X
Adverse Event Review and Evaluation 		X	X

1 hCG (urine) pregnancy test (all female subjects)

2 IV may be placed during screening/baseline to obtain qualifying venous sample at discretion of medical staff. If the IV is placed during screening/baseline, medical staff will offer to use local anesthetics.

3 Adverse events may be reported by the subject after their visit. See section 10 for additional details.

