  - 7.3.9. A venous sample will be obtained via needle stick or by placement of an IV and analyzed to verify that the subject meets the inclusion criteria for hemoglobin level. The subject will be excluded from the study if the values from the blood draw fall outside the ranges stated in the inclusion criteria.
  - 7.3.10. Subjects may have a blanket placed on them or hot water bottles placed under their hands.
  - 7.3.11. Subjects may be offered a snack (e.g., granola bar) and/or beverage (e.g., water, juice) due to the amount of time their involvement in this study may take.
- 7.4. **PROCEDURES**
- 7.4.1. Standard hospital-type monitors will be placed on the subject, including ECG and blood pressure, for safety monitoring by medical staff. The procedure will be stopped if there is any evidence of volunteer stress or distress. These signs include but are not limited to a rise or fall in mean arterial blood pressure of more than 30% from baseline, a rise in heart rate to more than 130 BPM, complaints of feeling faint, chest discomfort, GI distress, urinary discomfort or feelings of a bloated bladder, or alternation of mental status. Blood samples are also monitored for hemoglobin and/or blood oxygenation levels for subject safety.
  - 7.4.2. A peripheral venous line will be placed in the volunteer’s hand or arm. One or more venous sampling catheters will be used during the study for the removal of blood and administration of fluids.
  - 7.4.3. Local anesthetics such as lidocaine, ethyl chloride spray, or Pain Ease skin refrigerant spray may be used in the event that an IV is placed to numb the site. Subjects will be given the option to have lidocaine or numbing spray be used during IV placement for the purpose of making catheter placement more comfortable for the subjects.
  - 7.4.4. After intravenous access is established, one or more intra-arterial catheter(s) (arterial line or A-line) will be placed in the radial artery of the volunteer’s wrist. The A-line is placed to facilitate continuous blood pressure measurement for subject safety monitoring, to enable repeated removal of blood aliquots for reference hemoglobin values, [REDACTED]
  - 7.4.5. After arterial access is established, optical sensors for the noninvasive measurement(s) will be placed on the subject’s fingers.

- 7.4.6. Upon successful placement of the sensors and the volunteer’s indication that they are comfortable, a baseline set of blood samples will be obtained.
- 7.4.7. [REDACTED]

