- 7.4.8. Following removal of blood, the volunteer will rapidly receive intravenous fluid [REDACTED]
- 7.4.9. [REDACTED]
- 7.4.10. [REDACTED] blood samples [REDACTED] will be drawn at selected time intervals throughout the study while intravenous fluid is being administered for laboratory analysis of hemoglobin concentration. [REDACTED]
- 7.4.11. The total amount of blood removed from the subject may be up to [REDACTED]
- 7.4.12. [REDACTED]
- 7.4.13. The hemodilution procedure will continue until the subject’s fluid limits have been reached [REDACTED] or the target hemoglobin value has been reached.
- 7.4.14. At the conclusion of the procedure, the sensors/devices, IV(s) and the arterial line(s) will be removed and the volunteer will be allowed to leave after medical personnel determine it is safe to do so.
- 7.4.15. At the end of the hemodilution procedure, if the last arterial blood draw hemoglobin value is below 8.0 g/dL, then the subject’s hemoglobin level will be monitored using an FDA cleared pulse oximeter. Subjects who have a hemoglobin level below 8.0 g/dL must remain in the study area for observation and meet a minimum rise in hemoglobin of 0.5 g/dL prior to leaving the study area, or until medical staff determines it is safe to do so. If medical staff finds it is not safe to do so, the subject will be referred to an urgent care facility.
- 7.4.16. All volunteers will be encouraged to remain in the study area until they feel fit to leave. Subjects should feel safe and able before returning to work directly after participation in the study. Subjects who are employees of Masimo will be advised to take as much time as they need after the study before returning to work.
- 7.4.17. Volunteers will be given instructions on wound care. All volunteers will be instructed to contact the principal investigator in the event of any potential complication.
- 7.4.18. The total time for the study procedures will be up to [REDACTED]. [REDACTED]. Volunteers will be paid according to the compensation breakdown on the consent form.

- 7.4.19. Subjects will be provided with information related to any significant new findings that develop at any time during the study which may relate to their willingness to continue their participation, their health and/or medical care.

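### Does the 13.7 statement that blood withdrawal is confined to laboratory samples clash with the schedule's separate blood-removal row in a way that needs a change?

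*Combined protocol and SAP*

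**What the plan says.** Section 13.7 contrasts hemodilution in surgery with its use in the sponsor's clinical laboratory and states that in the latter "withdrawal and blood loss will be limited to samples required for laboratory analysis". The clause carries no condition. The word principally, later in the sentence, qualifies the purpose of hemodilution and not the limit on withdrawal.

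Elsewhere the protocol says:

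- **7.1 (Schedule of Activities):** Procedure Visit 1 has a row "Removal of Blood (if necessary") and a separate row "Continuous A-line sampling", the latter without a condition.
- **7.4.6:** once the sensors are in place, "a baseline set of blood samples will be obtained".
- **7.4.8:** "Following removal of blood, the volunteer will rapidly receive intravenous fluid"; the rest of the step is redacted.
- **7.4.10:** blood samples "will be drawn at selected time intervals throughout the study while intravenous fluid is being administered for laboratory analysis of hemoglobin concentration".
- **7.4.11:** "The total amount of blood removed from the subject may be up to" a limit whose value is redacted.
- **13.5:** blood removal has its own risk paragraph, which compares it with blood donation and adds: "Additionally, there is the risk of hypotension, tachycardia, anemia, dizziness and loss of consciousness".
- **13.6:** the risks of blood draws are covered under another heading.

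Steps 7.4.7, 7.4.9 and 7.4.12 are redacted in full.

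**The concern.** A reader who takes 13.7 at face value would conclude that no blood leaves the volunteer except what goes to the analyzers. The schedule suggests otherwise. The reference hemoglobin comes from repeated sampling, which every subject must have because it supplies the comparator for the only outcome. A step performed only when necessary therefore looks like something else. Section 7.4 has the same order: baseline samples, then removal, then fluid, then samples during the infusion.

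The subjects are healthy volunteers with no direct benefit (13.1). If the hemodilution risk statement described less blood loss than the procedure can involve, the IRB and staff would have two accounts of one intervention, and the volunteer's risk could be understated. That would be a matter of protection and not of statistics: nothing in the ARMS calculation in 9.2 uses the volume of blood removed.

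**Working it through.** No arithmetic on volumes is possible, because the limit in 7.4.11 is redacted and the number of subjects who would have the conditional step is not given. The check is a comparison of the passages.

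**1. Does 13.7 conflict with 7.1?** 13.7 is unconditional. 7.1 lists removal and sampling as two rows, one conditional and one not. The natural reading is that they are different procedures, and 13.7 makes no allowance for the first. This is the strongest evidence. It is not conclusive, because the sampling row names the arterial line only, so a conditional venous draw could still be a sample.

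**2. Does 7.4.8 confirm a separate step?** Only in part. It refers back to a removal, but the step just before it (7.4.7) is wholly redacted. The last visible event before it is the baseline sampling in 7.4.6. The protocol also uses removal for sampling: 7.4.4 applies the word to the arterial aliquots for reference hemoglobin, and 7.4.2 calls the lines used for removal venous sampling catheters. On the visible text alone, 7.4.8 could refer to the baseline samples.

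**3. Do the two risk headings prove two procedures?** No. 13.6 opens with needle puncture and bruising, whereas 13.5 adds the consequences of losing blood. Repeated sampling can involve both. The comparison with blood donation in 13.5 favors a separate step, but indirectly.

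**4. Is any risk left undisclosed?** 13.5 names 5 risks: hypotension, tachycardia, anemia, dizziness and loss of consciousness. 13.7 names 6: heart failure, respiratory failure, hypertension, edema, infection and electrolyte abnormalities. The overlap is 0 of 5, which is expected when one paragraph covers losing blood and the other covers receiving fluid. 13.6, which stands between them, lists close equivalents of four of the five (a sudden fall in blood pressure, a sudden rise in heart rate, lightheadedness and passing out). That leaves 5 − 4 = 1, anemia, named only in 13.5. All five are in the protocol, in the same section as 13.7.

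**5. Is there a limit?** Yes. 7.4.11 sets a ceiling on the total. The value is hidden from the public text but not absent from the plan.

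**6. Does the analysis change?** No. Bias and ARMS in 9.2 are computed from paired SpHb and reference hemoglobin values. How hemoglobin was lowered, by fluid alone or by removal plus fluid, does not enter either formula.

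**The case for a change.** The best case for acting is that redaction cannot rescue the sentence. If the hidden steps describe removal beyond samples, 13.7 is wrong for those subjects. If they confine removal to samples, the conditional row and the separate risk heading are misleading. Either way some visible text is out of line, 13.7 is an affirmative statement with no pointer to 13.5, and the correction costs a few words and an IRB submission.

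The first part stands: the visible wording is not fully consistent, and the ambiguity of the word removal does not comfortably explain a conditional row beside an unconditional one. The step from there to a needed change does not stand. Staff carry out the study from section 7.4 and the schedule, and nothing visible suggests that they would work from a background sentence in the risk section. The IRB receives the whole protocol, including the removal risks and the ceiling. The further questions, what makes removal necessary and whether the ceiling includes samples, may be answered in the redacted steps, so they cannot be treated as gaps.

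**Conclusion.** This is a slip in wording: one descriptive sentence in 13.7 is narrower than the schedule row in 7.1, with qualified support from 7.4.8 and indirect support from 13.5. Confidence that the visible passages do not fully agree is moderate, because part of the procedure is redacted and the key word is used in two senses.

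No change to the plan follows. A ceiling on blood removed exists, the risks of removal are disclosed, and neither the sample size nor the ARMS analysis is touched. If the protocol is reopened for another reason, the sentence and the schedule can be reconciled then. Which of them is right is for the investigator and the sponsor's medical staff.

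This rests on two assumptions: that the redacted steps contain the operating detail of removal, and that the consent form, which is not in the public text, carries the removal risks as 13.5 does. Had the protocol lacked either the ceiling or the 13.5 paragraph, the same mismatch would have been a matter of volunteer protection and would have needed correction.
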